In the cases of TWB-103/placebo discontinuation due to allergic reaction or infection, wound assessments performed after onset of

allergic reaction or infection will be excluded from statistical analysis.

Healing rates (complete wound closure) of patients at Days 7, 10 and 14 after DSW creation will be analyzed by CMH test. Healing percentage of wounds (ratio of healing and original areas) at Days 7, 10 and 14 after DSW creation will be analyzed by Analysis of variance (ANOVA) model with treatment group and country as factor. Score on short-form McGill pain questionnaire will be analyzed by using Analysis of covariance (ANCOVA) model with treatment group and country as factor and baseline characteristics as covariate. Vancouver Scar Scale will be analyzed by Wilcoxon ranked sum test. The score in each category (pigmentation, vascularity, pliability and height) and the sum score of all category in Vancouver Scar Scale will be analyzed.

All treatment group comparisons will be conducted with significance level of 0.05, using 2-tailed tests.

Demographics and baseline characteristics will be summarized for each group/country by using descriptive statistics.

[figure not shown]
SCHEDULE OF ASSESSMENTS

Procedure	Screening ¹	Treatment ^{12, 13}						Follow-up		
	Within 2 weeks prior to DSW creation	Day 0 ¹	Day 3 (± 1 day)	Day 7 (± 1 day)	Day 10 (± 1 day)	Day 14 (± 2 days) ¹⁴	Day 28 (± 3 days) ^{2,11}	Day 42 (± 3 days) ^{3,11}	90, 180, 270, 360 days (± 14 days) from visit 7 or 8 ^{4,11}	
Visit	1	2	3	4	5	6	7	8	9, 10, 11, 12	
Informed consent	X									
Screening no. assign	X									
Inclusion / Exclusion	X									
Randomization ¹⁹	X									
Demographics	X									
Medical History	X									
Physical Examination	X	X	X	X	X	X	X	X	X	
Vital Signs	X	X	X	X	X	X	X	X	X	
Pregnancy Test (Serum)	X									
PRA test: Class I HLA _a		X ²⁰						X		
Hemogram	X	X ²⁰	X	X	X	X	X	X		
Serum Biochemistry	X	X ²⁰	X	X	X	X	X	X		
TWB-103+Tegaderm TM or placebo+Tegaderm TM 5,6		X	X	X						
Tegaderm TM applying at site ⁶					X ⁷	X ^{7, 22}	X ^{7, 10, 22}			
Tegaderm TM dispensing ^{6, 8}		X	X	X	X	X ²²	X ^{22, 23}			
Tegaderm TM return ⁹			X	X	X	X ²²	X ²²	X ^{22, 23}		
Wound assessment ¹⁵		X	X	X	X	X	X ²	X	X ¹⁶	
Pain questionnaire ²¹	X		X	X	X	X	X	X	X	
AE assessment	X ¹⁷	X	X	X	X	X	X	X	X ¹⁸	
Prior/Concomitant treatment	X	X	X	X	X	X	X	X		
1. Visit 1 (screening) and Visit 2 (Day 0) can be performed on the same day.										

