4.3.2 Discontinue the study product

Patients who experience > Grade 2 skin allergic reaction or > Grade 2 systemic allergic reaction related to the product or placebo must not receive any further TWB-

103 or placebo treatment. If a patient should develop infection at DSW site before Day 10, he/she will stop the TWB-103 or placebo application at the investigator's discretion. Patients with the aforementioned conditions, before or at Visit 8, should finish the scheduled assessments (except that application of TWB-103/placebo is stopped; that the application and dispensation of Tegaderm™ will be at the investigator's discretion; and that the return of Tegaderm™ will be asked if applicable). Patients with allergic reaction or infection may receive appropriate treatments at the PI's discretion, will be monitored throughout the healing process (including the recovery from allergic reaction or infection, and the complete closure of DSW) and will continue the remaining visits (application of TWB-103 or placebo will be stopped if planned originally). In these cases of TWB-103/placebo discontinuation, wound assessments performed after onset of allergic reaction or infection will be excluded from statistical analysis.

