10.2 Statistical and Analytical Plans

10.2.1 Analysis Population

Two populations will be introduced for statistical analysis:

Intent-to-treat (ITT) population:

- Patients randomized
- Patients ever treated by at least one dose of trial medication
- Patients with any post-treatment evaluation

Per-protocol (PP) population:

- Dosed with planned dosing regimen of investigational product
- With efficacy endpoint measurement at wound assessment (with first 100% re-epithelialization or complete Day 14 visit evaluation)
- Fulfilling all inclusion and exclusion criteria
- Without taking prohibited medication

Since the dosing regimen designed in Phase I are exactly those designed for Phase II, and the procedures/schedules of assessment that patients receive are

identical in both phases, the data collected in Phase I portion will be combined with those in the Phase II portion for statistical analysis.

Primary endpoints and secondary efficacy endpoints in Phase I/II will be analyzed on ITT and PP population. Non-primary safety endpoints, demographics and baseline characteristics will be analyzed on ITT population. Conclusion of primary endpoint in Phase I will be made based on ITT population analysis results and that in Phase II will be made according to the result of ITT population analysis.

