10.2.2 Analysis methods

For all assessments, the baseline will be defined as the most recently available data before the administration of 1st dose treatment.

Descriptive statistics will be provided by treatment group/country and by all for all of the endpoints, including primary and secondary ones. Frequency table will be provided for categorical data, while mean, standard deviation, maximum, minimum, median, inter-quartile range (IQR), and 95% two-sided confidence interval will be calculated for continuous measurements.

AEs and SAEs will be reported by treatment group/country and physiological systems as appropriate. The incidence of treatment-related AEs and SAEs between treatments will be analyzed by Cochran-Mantel-Haenszel test (CMH) test.

Incidence of AEs and SAEs will be analyzed by CMH test. Changes in physical examinations will be displayed for each individual system. Net changes from pre-treatment laboratory test results and vital signs will be analyzed by descriptive statistics.

Healing time from DSW creation to 100% re-epithelialization will be estimated by using Kaplan-Meier methods and compared between groups by using log-rank test. The healing time is defined as from DSW creation to the first 100% re-epithelialization with confirmation for at least 10 days apart, observed by the investigator and the first additional evaluator.

If the first 100% re-epithelialization is observed at any visit by Day 28 with confirmation for at least 10 days apart, the healing time is noted as the duration from the Day of DSW creation to the day of the first 100% re-epithelialization. The fulfilling of the visits and/or follow-ups after the 100% re-epithelialization date will not be taken into account to determine the healing time. If the 100% re-epithelialization is not observed by Day 28 visit, the healing time will be censored on day of the last visit up to Day 28 visit. If the 100% re-epithelialization is observed by Day 28 visit but no confirmation is made, the healing time will be censored on day of the last visit up to Day 28 visit. The censoring rules will be applied immediately once patients leave the study regardless the participation and/or completion of the long-term (360 days) follow-ups.

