If patient develops grade 2 or above SAEs and should exit the study prematurely before Day 14, he/she should be excluded from the primary efficacy analysis, because early censor will result in under estimation of the healing time while treatment group (TWB-103+TegadermTM) is prone to have higher risk of developing treatment related SAE.

In the cases of TWB-103/placebo discontinuation due to allergic reaction or infection, wound assessments performed after onset of allergic reaction or infection will be excluded from statistical analysis.

Healing rates (complete wound closure) of patients at Days 7, 10 and 14 after DSW creation will be analyzed by CMH test. Healing percentage of wounds (ratio of healing and original areas) at Days 7, 10 and 14 after DSW creation will be analyzed by Analysis of variance (ANOVA) model with treatment group and country as factor. Score on short-form McGill pain questionnaire will be analyzed by using Analysis of covariance (ANCOVA) model with treatment group and country as factor and baseline characteristics as covariate. Vancouver Scar Scale will be analyzed by Wilcoxon ranked sum test. The score in each category (pigmentation, vascularity, pliability and height) and the sum score of all category in Vancouver Scar Scale will be analyzed.

All treatment group comparisons will be conducted with significance level of 0.05, using 2-tailed tests.

Demographics and baseline characteristics will be summarized for each group/country by using descriptive statistics.

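### The primary efficacy analysis drops ITT patients who leave before Day 14 with a grade 2+ SAE, and the stated reason (early censoring) does not support the exclusion under Kaplan-Meier

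*Combined protocol and SAP*

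**What the plan says.** Section 10.2.2 compares healing time by Kaplan-Meier and log-rank. A patient with no complete re-epithelialization by Day 28 is censored at the last visit up to Day 28. Unconfirmed closure is handled the same way: if it is "observed by Day 28 visit but no confirmation is made, the healing time will be censored" as well. The section adds: "The censoring rules will be applied immediately once patients leave the study".

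It then makes an exception. For a patient with a grade 2 or higher SAE, related or not, who exits before Day 14, it says "he/she should be excluded from the primary efficacy analysis, because early censor will result in under estimation of the healing time", and adds that the TWB-103 group is more prone to treatment-related SAEs. The Protocol Summary (Statistical Analysis) repeats the rule.

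Section 10.2.1 defines ITT as randomized, dosed at least once and with any post-treatment evaluation. Nothing in that definition removes SAE exits. On the efficacy conclusion it says "that in Phase II will be made according to the result of ITT population analysis".

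Section 3.4 and note 11 to the Schedule of Assessments require patients withdrawn before Day 28 to complete the Day 28 assessments. Section 10.2.5 rules out imputation.

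**The concern.** There are two problems.

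First, the comparison on which the conclusion rests is not made on the ITT set that section 10.2.1 names. Patients who meet that definition are removed because of something that happened after randomisation, and the plan says that a closely related event will be commoner in one arm. No analysis that keeps these patients is described.

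Second, the rule is justified as protection against under-estimating healing time. If that reason fails, the plan gives up part of the randomised comparison and gets nothing in return. If the patients who leave are slow healers, the rule leaves the feared bias in place or slightly enlarges it, in favour of the arm that loses more patients.

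**Working it through.** **No plan figure to reproduce.** The documents give no power calculation, event rate or SAE-exit rate; the sample size is described as arbitrary and as clinical judgment. The direction below follows from the method. The sizes rest on assumed data.

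**Direction.** The Kaplan-Meier proportion unhealed is S(t) = Π(1 − d/Y), with d healing events and Y patients at risk at each event time. Suppose k patients would be censored at exit. At event times up to exit they count in Y, so the hazard is d/n with censoring and d/(n − k) with exclusion. After exit the hazards are equal. Excluding them therefore gives the same curve (exit before the first healing event) or a faster one. A check on 20,000 random small data sets found no exception.

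**Who would be censored.** Visit 4 is Day 7 ± 1, so closure first seen there dates from Day 6 at the earliest. Confirmation at least 10 days apart then falls on Day 6 + 10 = Day 16, after any exit before Day 14. Section 1.1 expects spontaneous healing in 7 to 21 days, so closure early enough to be confirmed before exit is not realistic. Both unhealed and healed-but-unconfirmed exits are therefore censored, unless a post-withdrawal assessment counts as confirmation.

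**Size, assumed TWB-103 arm of 15.** Closures: 2 at Day 7, 3 at Day 10, 5 at Day 14, 2 at Day 28; 1 never closes; 2 exit with an SAE. Events precede censorings at ties. Proportion healed at Day 14:

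- Excluded (n = 13): S = 11/13 × 8/11 × 3/8 = 3/13, so 76.9%.
- Censored at Day 3: both leave before any event, so again 76.9%.
- Censored at Day 7: S = 13/15 × 8/11 × 3/8 = 0.236, so 76.4%.
- Censored at Day 10: S = 13/15 × 10/13 × 3/8 = 0.250, so 75.0%.

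The gap is 0 to 1.9 points (76.92 − 75.00 = 1.92). Mean healing time restricted to 28 days is 15.2 days excluded, against 15.2, 15.4 and 15.8 days censored at Days 3, 7 and 10.

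**Test.** Take an assumed control arm of 15 with no exits: 1, 2, 5 and 5 close at Days 7, 10, 14 and 28, and 2 never close. Log-rank z is 1.24 excluded, and 1.24, 1.18 and 1.06 censored at Days 3, 7 and 10. Two-sided p is 0.22 against 0.22 to 0.29.

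**Bounds from other handling.**

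- Both exits closed at Day 10 and confirmed after exit: S = 13/15 × 8/13 × 3/8 = 3/15, so 80.0%, or 80.00 − 76.92 = +3.1 points against exclusion.
- Both kept as unhealed to Day 28: S = 5/15, so 66.7%, or 66.67 − 76.92 = −10.3 points. This is a different estimand.

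**Simulation.** Assumptions: no treatment effect, 18 per arm, median healing 12 days, exits on TWB-103 only, 20,000 trials per setting. When the exits were the slowest healers, the false-positive rate favouring TWB-103 (nominal 2.5%) was:

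| Exits | Censored | Excluded |
|---|---|---|
| 1 | 4.6% | 5.0% |
| 2 | 7.6% | 8.9% |
| 3 | 11.4% | 14.0% |

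When exit was unrelated to healing, the restricted mean was 17.33 to 17.37 days with exclusion and 17.42 to 17.66 with censoring, against about 17.34 without exits. Censoring did not under-estimate there.

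**The case against.** **The practical weight is small.** The rule needs both a grade 2+ SAE and study exit before Day 14. An SAE is not itself a listed withdrawal criterion in section 3.4. Under section 4.3.2, patients who stop product for allergy or infection "will continue the remaining visits (application of TWB-103 or placebo will be stopped if planned originally"), so they have not left the study. The rule is pre-specified and applies to both arms. The per-protocol set already asks for patients "with first 100% re-epithelialization or complete Day 14 visit evaluation", so most unhealed early exits leave that set anyway and the rule acts mainly on the ITT analysis. All of this stands, and it limits the size of the point.

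**Exclusion can be unbiased.** If exit is unrelated to healing, exclusion shows no bias in the simulation, while censoring unconfirmed closures makes healing look slightly slow. That also stands. But there is then no under-estimation to prevent, so the stated reason still fails.

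**Early censoring does shorten a raw average.** A simple mean that treats censored times as healing times would be too short, and exclusion would remove those values. The primary analysis, however, is Kaplan-Meier and log-rank.

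**The direction can reverse.** Closure by Day 14 is normally confirmed at Day 28, and withdrawn patients are asked to complete that visit. If it counts, exclusion may discard a confirmed early healing on TWB-103. This stands, and the plan does not settle whether the visit counts.

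**Stronger readings to avoid.** A reader might infer that the rule always flatters TWB-103. The documents do not support that, because of the confirmation route just described. A reader might also take the 10.3-point gap to the 66.7% bound as the bias. It is not: the bound treats every exit as unhealed to Day 28. Dating closure first seen at a post-withdrawal Day 28 visit as Day 28 gives the same Day 14 figure simply because the Day 10 and Day 14 visits were missed.

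**Conclusion.** The point holds, with limited size. The exclusion departs from the ITT basis of the conclusion and selects on an event that the plan expects to differ by arm. For patients who would otherwise be censored, it cannot reduce the under-estimation it is meant to prevent. That part is algebra and does not depend on the example.

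The size does depend on assumptions: in the worked example, 0 to 1.9 points healed at Day 14, with no change in the significance conclusion. Without qualifying exits the effect is nil. The text should be corrected, but nothing in the documents shows that the primary result would be materially distorted.

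**What to change.** 1. Delete the exclusion sentence in section 10.2.2 and in the Protocol Summary. Keep all ITT patients in the primary Kaplan-Meier and log-rank analysis, and censor those without confirmed healing at their last visit before exit under the existing rule.
2. Report the exclusion analysis as a sensitivity analysis.
3. State whether the Day 28 assessments required after withdrawal (section 3.4; Schedule of Assessments, note 11) count, given that censoring is to apply as soon as a patient leaves. If they count, use them in the primary analysis only to confirm closure already seen before exit. Put closure first seen at that visit, dated as Day 28, in a sensitivity analysis.
4. If exits are also counted as unhealed to Day 28, label this a conservative sensitivity analysis with a different estimand, and state the exception to the censoring and no-imputation rules.

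The cost is wording in two places and one or two short analyses. With plain censoring, the TWB-103 estimate is unchanged or slightly less favourable (0 to 1.9 points in the example). If post-exit confirmation counts, it can instead move in favour of TWB-103 (up to +3.1 points there). Informative censoring remains wherever no post-exit assessment is obtained, and the report should say so.

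### The ITT healing analyses discard wound assessments collected after an allergic reaction or infection stops the product, and neither reading of the censoring rule recovers the observed outcome

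*Combined protocol and SAP*

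**What the plan says.** **The rule.** Section 4.3.2 stops the product for a skin or systemic allergic reaction above Grade 2 related to product or placebo. For a donor-site infection before Day 10, "he/she will stop the TWB-103 or placebo application at the investigator's discretion". In these discontinuations, "wound assessments performed after onset of allergic reaction or infection will be excluded from statistical analysis". The sentence stands in 4.3.2, in 10.2.2 and twice in the Protocol Summary (Study Design and Statistical Analysis). It names no analysis population.

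**The data are still collected.** Under 4.3.2 these patients finish scheduled assessments, are followed through healing, and "will continue the remaining visits (application of TWB-103 or placebo will be stopped if planned originally".

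**Population and method.** Section 10.2.1 analyses efficacy on ITT and PP and draws the conclusion from ITT. Section 10.2.2 uses Kaplan-Meier and the log-rank test. If closure is not observed by the Day 28 visit, or is observed but not confirmed, "the healing time will be censored on day of the last visit up to Day 28 visit". Section 10.2.5 rules out imputation.

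**The plan's own view of early censoring.** For patients who exit early with a serious event, 10.2.2 gives as its reason that "early censor will result in under estimation of the healing time", and adds that the treatment group "is prone to have higher risk of developing treatment related SAE".

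**Scar data.** At Visits 9–12 the wound assessment consists of scar, skin-texture and sensation assessment (Schedule of Assessments, note 16; section 6.11).

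**The concern.** A wound infection or allergic reaction happens after randomization and bears on healing. Removing what was observed afterwards, in patients who stay in the trial, takes away much of what an ITT analysis protects. The censoring sentence also does not say whether an attended visit counts as the last visit once its wound assessment is excluded. The same patient can therefore enter the primary analysis in two very different ways, and neither matches what was seen. If the choice is left until data are in hand, the primary result could depend on it. With about 36 patients recruited 1:1, one patient is 1/18 = 5.6 percentage points of an arm, if all 36 enter ITT.

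**Working it through.** The plan states no figure that depends on this rule, so there is nothing to reproduce.

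**Step 1: one patient.** Infection on Day 5, product stopped, closure first seen on Day 14 and confirmed on Day 28 (14 days apart, so the 10-day requirement is met).

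| Handling | Entry in the primary analysis |
|---|---|
| All collected assessments | Event at Day 14 |
| Excluded; last attended visit (literal reading) | Censored at Day 28 as unhealed |
| Excluded; last visit before onset | Censored at Day 3 |

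**Step 2: other endpoints.** With no imputation, this patient is missing from the Day 7, 10 and 14 healing rates and healing percentages. Read literally, the rule also removes the Vancouver Scar Scale at Visits 9–12. Pain and adverse-event data are untouched.

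**Step 3: how often.** No rate is given. The chance that at least one of 36 patients is affected is 1 − (1 − p)^36: 30% at p = 1%, 67% at 3%, 84% at 5%.

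**Step 4: illustrative size.** All inputs here are assumptions. Unaffected wounds heal alike in both arms, lognormal with median 14 days and log-SD 0.35. A share q1 (TWB-103) or q0 (placebo) is affected early, and healing in those patients is delayed by d days. F(t) is the proportion of unaffected wounds healed by day t:

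- F(28) = Φ(ln 2 / 0.35) = 0.976
- F(21) = Φ(ln 1.5 / 0.35) = 0.877
- F(14) = 0.500

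Difference in Kaplan-Meier proportion healed at Day 28, TWB-103 minus placebo:

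- all data: −(q1 − q0) × [F(28) − F(28 − d)]
- last attended visit: −(q1 − q0) × F(28)
- last visit before onset: 0, because affected patients leave the risk set before they can contribute

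| Affected | Delay | All data | Last attended visit | Before onset |
|---|---|---|---|---|
| 10% v 5% | none | 0.0 | −4.9 | 0.0 |
| 10% v 5% | 7 days | 0.05 × (0.976 − 0.877) → −0.5 | −4.9 | 0.0 |
| 10% v 5% | 14 days | 0.05 × (0.976 − 0.500) → −2.4 | −4.9 | 0.0 |
| 20% v 5% | none | 0.0 | −14.6 | 0.0 |
| 20% v 5% | 7 days | −1.5 | −14.6 | 0.0 |
| 20% v 5% | 14 days | −7.1 | −14.6 | 0.0 |
| 20% v 5% | never closes | −14.6 | −14.6 | 0.0 |

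A simulation of 40,000 trials per scenario, 18 per arm, with closure seen only at scheduled visits, agrees (20% v 5%, 14 days: −7.2 / −14.6 / −0.1). Equal rates (10% or 20% in both arms) give zero on all three within 0.14 point. Reversing the arms reverses the sign.

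**Step 5: the log-rank test.** Chance of a significant result against TWB-103 with a 14-day delay (nominal 2.5% in one direction), in the order all data / last attended visit / before onset:

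- 10% v 5%: 4.1% / 4.9% / 2.3%
- 20% v 5%: 9.4% / 14.9% / 2.3%
- 3% v 1%: 2.9% / 3.2% / 2.5%

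With healing uniform over the 7 to 21 days given in section 1.1, 20% v 5% affected and a 7-day delay, the figures are 7.0% / 15.8% / 2.2%: the same ordering.

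**The case against.** **Few patients.** The product is applied only at Visits 2–4 (5.5, 6.10), and eligibility screens out infection-prone sites and known sensitivities. This stands: at 3% v 1% the effect is hardly visible.

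**The text already settles the date.** The rule excludes assessments, not visits, and these patients keep attending, so the last visit is literally the last one attended. That is the more natural reading. It does not rescue the rule, because it counts as unhealed a patient whose closure was seen and confirmed. It could be defended as a composite that treats a complication stopping treatment as failure to heal, but the plan does not say that it intends this.

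**The Day 28 proportion is not a listed endpoint.** Correct. On the Kaplan-Meier curve at Day 14, with 20% v 5%, all data and the literal reading nearly agree at a 7-day delay (−7.2 v −7.6) and a 14-day delay (−7.3 v −7.3). They differ with no delay (0.0 v −7.5). The log-rank test uses the whole curve.

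A reader might also infer stronger points that the documents do not support:

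- **A healed patient loses the event because confirmation falls after onset.** The phrase "Patients with the aforementioned conditions, before or at Visit 8" governs finishing assessments. Application already stops at full re-epithelialization (Schedule of Assessments, notes 5 and 12), so a healed patient has almost no product left to discontinue.
- **Two rules collide for one case.** A patient with a serious event who "should exit the study prematurely before Day 14, he/she should be excluded from the primary efficacy analysis" is out of that analysis, so the assessment exclusion is moot there.
- **The rule touches ITT only.** The summary allows 2 to 3 applications, so a patient stopped after two might remain in PP.
- **Discretion over stopping favours an arm.** Patients and investigator are blinded (4.2); discretion adds inconsistency, not in itself arm-dependent handling.

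**Conclusion.** The concern holds and should be fixed before unblinding. Followed as written, the plan discards collected outcomes from the ITT analysis after a post-randomization event related to healing, and neither available censoring date returns the observed result. Censoring before onset is the early censoring that 10.2.2 itself warns about.

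This conclusion rests on the text, not on the simulated sizes, whose event rates and delays are assumed. Between-arm bias needs event rates, or effects on healing, that differ between arms; with equal rates and effects there is none. The literal reading matches the all-data result only if affected wounds never close by Day 28. Censoring before onset matches it only if there is no delay. Between those extremes the two depart from it on opposite sides; at the extremes they do not, so it would be wrong to say that they always pull in opposite directions. Nor should a reader infer that the rule is known to work against TWB-103: the plan expects an imbalance in treatment-related serious events only, and gives no rate.

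**What to change.** In 10.2.2, in 4.3.2 and at both places in the Protocol Summary, replace the exclusion sentence with:

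> The ITT wound-healing analyses use all wound assessments collected up to Day 28, and the Day 42 re-confirmation, whether or not TWB-103/placebo was discontinued, under the event and censoring rules applied to all patients. Scar assessments at Visits 9–12 are likewise retained. As labelled sensitivity analyses, patients whose product was discontinued for allergic reaction or infection are (a) censored at the last wound assessment before onset and (b) counted as unhealed to Day 28.

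Leave the separate sentence on exits for serious events out of this change. If the sponsor prefers to keep the exclusion in its main analysis, it should at least name the censoring date and add the all-data ITT analysis.

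The cost is wording and two extra analyses; the visits and assessments are already scheduled. The downside is that the ITT estimate then includes the effect of treatment given for the complication, which the sensitivity analyses help to show. No change to clinical management is proposed.
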